9.4.2. Primary Endpoint(s)

The primary endpoint of the study is change in pVO_2 by CPET from baseline to Week 24.

The primary estimand is the difference in means of the change from baseline to Week 24 in pVO_2 between CK-3773274 and placebo for the target population of potentially treatable CK-3773274 patients despite intercurrent events after a first dose. Missing data will be imputed using multiple imputation method under the missing at random (MAR) assumption. The

distribution of missing CPET data at Week 24 and the reasons for the missing data will be tabulated in the FAS. The primary analysis of the primary endpoint will use an ANCOVA model with treatment group, randomization stratification factors, baseline pVO₂ and baseline weight as covariates in the FAS. Sensitivity analyses will be performed by repeating the primary analysis examining assumptions that data are not missing at random: missing pVO₂ from patients who discontinued CK-3773274 treatment or missing pVO₂ from patients from the placebo arm will be imputed based on the model that is constructed using observed pVO₂ data from the placebo arm. Missing pVO₂ from patients who remained on CK-3773274 treatment will be imputed based on the model that is constructed using observed pVO₂ data from the CK-3773274 arm. The LSMs, LSM treatment difference, and the standard error from each imputed dataset will be combined using Rubin's rules to produce an overall LSM estimate of the treatment difference, its 95% confidence interval, and p-value.

Other sensitivity analyses and the details will be included in the SAP.

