The imputation model will use regression multiple imputation which includes treatment group, randomization stratification factors, baseline pVO₂, sex, age, baseline hemoglobin, baseline body weight, baseline KCCQ CSS, and baseline NYHA class and the last available post randomization NYHA functional class, resting and Valsalva LVOT. Categorical variables, i.e., treatment group, baseline NYHA functional class, and sex will be specified in the CLASS statement. One hundred

(100) imputed datasets will be generated. Change from baseline in pVO₂ will be calculated based on the observed and imputed data. Each of the imputed dataset will be analyzed using the primary analysis ANCOVA model. LSM estimate of treatment difference and the standard error will be combined using Rubin's rules ([Rubin 1987](#)) to produce a LSM estimate of the treatment difference, its 95% confidence interval, and p-value for the test of null hypothesis of no treatment effect. LSM, LSM difference and the corresponding standard error, 95% CI and p-value will be presented.

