7.7.2. Sensitivity Analyses of the Primary Efficacy Endpoint

To evaluate the robustness of the primary analysis approach, sensitivity analyses, e.g., placebo-based imputation and tipping point analysis will be performed. In placebo-based imputation, missing pVO₂ from subjects who discontinued from aficamten treatment or missing pVO₂ from subjects from the placebo arm will be imputed based on the model that is constructed using observed pVO₂ data from the placebo arm. Missing pVO₂ from subjects who remained on aficamten treatment will be imputed based on the model that is constructed using observed pVO₂ data from aficamten arm. Tipping point analysis will be performed by applying a range of negative shift to adjust the imputed value of missing pVO₂ in aficamten group. If there are 10% or more missing data and/or 5% or more subjects missing data due to reason related to IP, the primary analysis will have the missing data imputed using placebo-based imputation.

The tipping point can be identified while the result is no longer statistically significant. Clinical judgment will be applied to evaluate the plausibility of the assumptions underlying this tipping point.

In addition, sensitivity analysis to evaluate COVID-19 impact will be performed by repeating the primary analysis after setting the Week 24 CPET to missing from subjects who are impacted by COVID pandemic.

Another sensitivity analysis is to fit a repeated measures mixed model to pVO₂ baseline and Week 24 data. The model includes stratification factors, visit, stratification by visit, and a numeric covariate which equals 0 for both treatment groups at baseline and equals 0 for placebo at Week 24 and equals 1 for aficamten group at Week 24. The primary treatment comparison is for the numeric covariate for treatments which corresponds to the treatment difference at week 24 in a specification for which there is no treatment difference at baseline.

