7.8.1. Analysis of the Secondary Efficacy Endpoints

1. Change in KCCQ-CSS from baseline to Week 12 and Week 24

The primary analysis for change in KCCQ-CSS from baseline to Week 12 and 24 will be performed using a MMRM model with baseline as covariate, randomization stratification factors, visit, treatment group, and interaction terms of treatment by visit and baseline by visit. An unstructured covariance matrix will be specified. All data observed up to Week 24 post randomization will be included in the model. Estimates for endpoints at Week 12 and Week 24 will be obtained from the LS Means estimate at visit of Week 12 and 24 from the model.

If there are >10% difference in baseline KCCQ CSS across regions, treatment by visit and region, baseline by visit and region will be included in the model. Treatment effect at each visit

week will be estimated from the interaction terms of treatment by visit by region, with coefficients for each region determined by proportion of patients evaluated in each region.

Sensitivity analysis based on multiple imputation with one hundred invocations will be performed. First the intermittent missing data will be imputed using the Markov Chain Monte Carlo (MCMC) method under MAR assumption. The imputation will be performed separately for each randomized treatment group and will include the following terms in the imputation model: region (for KCCQ only), endpoint observations from baseline up to Week 24. The monotone missing data will be imputed using the imputation model built from placebo group. 100 complete data sets will be generated and analyzed using the same model for the primary analysis of the change from baseline endpoint. The results from the 100 complete data sets will be combined using Rubin's combination rule for the inference.

Subgroup analysis will be performed using the primary analysis model MMRM model including additional effects of subgroup, subgroup by treatment and subgroup by treatment by visit interaction the model.

2. Change from baseline in post-Valsalva LVOT-G from baseline to Week 12 and Week 24

The analysis of this endpoint will follow the same specified above for change in KCCQ-CSS change from baseline to Week 12 and 24.

3. Proportion of patients with ≥ 1 class improvement in NYHA Functional Class at Weeks 12 and Week 24

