Change in KCCQ-CSS from baseline to Week 12 and Week 24	MMRM model with baseline as covariate, randomization stratification factors, visit, treatment group, and interaction terms of treatment by visit and baseline by visit. An unstructured covariance matrix will be specified.	Sensitivity analysis: 
 Intermittent missing data be imputed using multiple imputation MCMC first and the monotone missing values will be imputed using the imputation model built from the placebo group. Complete data will be analyzed using ANCOVA model for each week separately. Subgroup analyses for variables in Section 7.5	
Change in post-Valsalva LVOT-G from baseline to Week 12 and Week 24	MMRM model with baseline as covariate, randomization stratification factors, visit, treatment group, and interaction terms of treatment by visit and baseline by visit. An unstructured covariance matrix will be specified.	Sensitivity analysis: 
 Intermittent missing data be imputed using multiple imputation MCMC first and the monotone missing values will be imputed using the imputation model built from the placebo group. Complete data will be analyzed using ANCOVA model for each week separately, Subgroup analyses for variables in Section 7.5	
Proportion of patients with ≥ 1 class improvement in NYHA Functional Class from baseline to Week 12 and Week 24	CMH test stratified by randomization factors	Treating patient as non-responder if NYHA is not performed and repeat CMH test. Subgroup analyses for variables in Section 7.5	

Table 6: Endpoint Summary Table (Continued)

Endpoint	Primary Analysis Method	Sensitivity/Subgroup Analysis	COVID-19 Related Analyses
Proportion of patients with post-Valsalva LVOT-G <30 mmHg	CMH test stratified by randomization factors	Subgroup analyses for variables in Section 7.5	

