11.5. Sample SAS Codes

ANCOVA model for primary endpoint

```
proc mixed data=work;  
  class <treatment arm (ref='0')> <Beta Blocker use> <Exercise Modality>;  
  model chg=<base pvo2 > <base weight> <treatment arm> <beta blocker use> <Exercise  
  Modality> /solution s Influence(EFFECT=usubjid) outp=out vciry;  
  lsmeans <treatment arm>/pdiff cl;  
  ods output solutionf=mixparms covB=mixcovb;  
run;
```

This code assumes that the analysis involves 2 levels in treatment arm (e.g., placebo group is coded as 0 and aficamten is coded as 1).

MMRM model

```
proc mixed data=work;  
  class <Subject> <treatment arm (ref='0')> <Beta Blocker use> <Exercise Modality> <visit>;  
  model <chg> = <base> <treatment arm> <visit> <visit>*<treatment arm> <Beta Blocker use> <Exercise  
  Modality> <visit>*<base>/ddfm=kenwardroger;  
  repeated <visit> / type=un subject=<Subject>;  
  lsmeans <visit>*<treatment arm>/cl pdiff;  
run;
```

This code assumes 2 level in treatment arm with placebo group is coded as 0. visit has level of nominal visit week where continuous measurements are assessed up to Week 24.

Imputation model for primary endpoint

```
proc mi data=work seed=&seed out=miout NIMPUTE=50;  
  class <treatment arm> <Beta Blocker use> <Exercise Modality> <base NYHA> <randomization  
  factors>;  
  var <treatment arm> <randomization stratifications> <sex> <age> <base pVO2> <base  
  hemoglobin> <base KCCQ CSS> <baseline NYHA> <last available post rand NYHA> <last  
  available post rand resting LVOT> <last available post rand Valsalva LVOT> <W24 pVO2> ;  
  monotone reg(W24 pVO2);  
run;
```

Placebo-based imputation for sensitivity analysis of the primary endpoint

Step 1:

generate input dataset for subjects in placebo group or subject who didn't complete treatment, and datasets for the rest of subjects in aficamten group.

Step2: impute missing data with separately with each input dataset using the imputation model for the primary endpoint.

Step 3. Combined the complete data from the imputations above as final imputed dataset.

Tipping point imputation for primary endpoint

```
proc mi data=work seed=&seed out=miout NIMPUTE=50;  
  class <treatment arm> <Beta Blocker use> <Exercise Modality> <base NYHA> <>;  
  var <treatment arm> <sex> <age> <base pVO2> <base hemoglobin> <base KCCQ CSS>  
  <baseline NYHA> <last available post rand NYHA> <last available post rand resting LVOT>  
  <last available post rand Valsalva LVOT> <W24 pVO2> ;  

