  monotone reg(W24 pVO2);  
  mmar adjust (W24 pVO2/shift=&shift adjustobs=(Trt='1'));  
run;
```

shift will be set so that the imputed value for aficamten group is 1 ml/min/kg worse as starting point with increment of 1 ml/min/kg worse each time until the result is no longer significant.

Multiple Imputation for sensitivity analysis for repeated measures endpoint

Step 1:

```
proc mi data=work1 seed=&seed1 out=miout1 NIMPUTE=100;
  by <treatment arm>;
  mcmc IMPUTE=monotone ;
  var <base> <var week 2> <var week4> <var week6> <var week8> <var week12> <var week16>
<var week20> <var week24>;
run;
```

Step 2:

```
proc mi data=miout1 seed=&seed NIMPUTE=1 OUT=miout2;
  class <treatment arm>;
  by _IMPUTATION_;
  var <treatment arm> <base> <var week 2> <var week4> <var week6> <var week8> <var week12> <var
week16> <var week20> <var week24>;
  monotone reg (<base> <var week 2> <var week4> <var week6> <var week8> <var week12> <var
week16> <var week20>);
  mmar model (<base> <var week 2> <var week4> <var week6> <var week8> <var week12> <var
week16> <var week20> / modelobs = (trt01pn = '0'));
run;
```

Multiple Imputation for categorical endpoint

```
proc mi data=work seed=&seed out=outwork NIMPUTE=100;
  class <var at week8> < var at week 12> < var at week 16> < var at week 20> < var at week 24>
<treatment arm>;
  var <treatment arm> <var at week8> < var at week 12> < var at week 16> < var at week 20> < var at
week 24> ;
  fcs logistic (<var at week8> < var at week 12> < var at week 16> < var at week 20> < var at week 24> =
<treatment arm> /link=glogit);
run;
```

SAS codes using proc mianalyze to combine results from imputed datasets

The pooled estimates from the 50 imputed datasets are obtained from the following codes.

```
proc mianalyze data=est;
  modeleffects estimate;
  stderr stderr;
run;
```

Mixed model for CPET data

```
proc mixed data=work;
  class <subject ID> <visit> <stratification factors> ;
  model <chg in CPET>=<trtid> <stratification factors> <stratification factors>*<visit> /s;
  estimate 'active at Week 24' int 1 <trtid> 1 <stratification factors> &c1 &c2 stratification
factors>*<visit> 0 0 &c1 & / e;
  estimate 'placebo at Week 24' int 1 <trtid> 0 <stratification factors> &c1 &c2 stratification
factors>*<visit> 0 0 &c1 & / e;
  estimate 'active vs PBO at Week 24' trt 1;
  repeated <visit>/subject=<subject id> type=un;
run;
```

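### Template code in SAP 11.5 does not carry out analyses the SAP text specifies: Week 24 is left out of the placebo-based imputation for KCCQ-CSS and LVOT-G, and two pVO2 templates are out of step

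*SAP*

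**What the plan says.** **KCCQ-CSS and post-Valsalva LVOT-G sensitivity analysis.** SAP 7.8.1 first fills intermittent gaps by MCMC within arm, then states: "The monotone missing data will be imputed using the imputation model built from placebo group". LVOT-G follows the same method. Table 6 repeats the rule for both endpoints: "the monotone missing values will be imputed using the imputation model built from the placebo group". Neither place excepts a visit. In SAP 11.5, Step 2 of the repeated-measures code closes its placebo-restricted list at Week 20: "week16> <var week20> / modelobs = (trt01pn = '0".

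**Primary pVO2 imputation.** SAP 7.7.1 specifies 100 imputed datasets and a regression model whose terms include baseline body weight. The 11.5 code for this model sets `NIMPUTE=50`, and its variable list has no weight term. The text that introduces the combining step also refers to 50 datasets.

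**Mixed-model sensitivity analysis.** SAP 7.7.2 fits a repeated measures model to the baseline and Week 24 pVO2 data. The 11.5 code takes change in CPET as the response, with an unstructured covariance over visits.

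**pVO2 placebo-based imputation.** SAP 7.7.2 says missing values from aficamten discontinuers and "subjects from the placebo arm will be imputed based on the model that is constructed using observed" placebo data; Protocol 9.4.2 says the same ("patients from the placebo arm will be imputed based on the model that is constructed using observed"). Table 6 treats discontinuers as though they were in the placebo arm. The worded steps in 11.5 begin "generate input dataset for subjects in placebo group or subject who" did not complete treatment, and then "impute missing data with separately with each input dataset using the imputation model for the primary endpoint". In 7.7.1 that model has an arm term: "The imputation model will use regression multiple imputation which includes treatment group".

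**The concern.** The text and the code describe different analyses, and no passage says which governs. A programmer working from 11.5 would produce a KCCQ-CSS and LVOT-G sensitivity analysis that is labelled placebo-based but is not placebo-based at Week 24. Week 24 is where these endpoints are tested first (Steps 2 and 4 of the hierarchy), so it is the visit at which a check on the missing-data assumption matters most.

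The two pVO2 mismatches are of the same kind. The imputation template is leaner than the model in the text, and the mixed-model template cannot do what 7.7.2 describes. If a programmer notices and repairs any of this, the choice is made outside the plan.

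**Working it through.** The plan states no figure on this point to reproduce. The check compares the lists and then sizes the consequence under stated assumptions.

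**1. Lists in Step 2 of the repeated-measures code**

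| Statement | Visits listed |
|---|---|
| VAR | arm, baseline, Weeks 2, 4, 6, 8, 12, 16, 20, 24 |
| `monotone reg` | baseline, Weeks 2, 4, 6, 8, 12, 16, 20 |
| placebo-restricted model | baseline, Weeks 2, 4, 6, 8, 12, 16, 20 |

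Week 24 is the only visit in VAR that is missing from both other lists. Each of those lists closes with its own syntax after Week 20, so this is not a gap in the extracted text. Week 12 is in all three.

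**2. Size at Week 24.** The documents do not say how the software treats an unlisted variable.

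- Assumption: it imputes Week 24 by ordinary regression on arm, baseline and the seven earlier visits.
- Relative to the placebo model, each aficamten dropout's Week 24 value is then raised by the arm coefficient, which is (effect at Week 24) - b'(effects at earlier visits).
- Under compound symmetry with correlation r, each of the eight regression weights is r/(1+7r).

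With effects expressed as a fraction of the Week 24 effect:

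- Full effect from Week 2, r = 0.8: 1 - 7(0.8)/6.6 = 1 - 0.848 = 0.152.
- Effect linear to Week 12 and then flat, r = 0.6: the earlier effects sum to (2+4+6+8)/12 + 3 = 4.667, and 1 - 4.667 x 0.6/5.2 = 1 - 0.538 = 0.462.

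Across compound symmetry, AR(1) and their average, r = 0.6, 0.7 and 0.8, and effects complete at Week 2, 8 or 12, the coefficient runs from 0.151 to 0.462. At an assumed 5-10% dropout the overstatement is 0.05 x 0.151 = 0.8% to 0.10 x 0.462 = 4.6% of the effect.

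A separate large-sample simulation used the same software assumption, a true effect of 0.50 SD and 10% monotone missing per arm. The code as printed exceeded the full placebo model by 0.006 to 0.026 SD, which is about 1-5% of 0.50.

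**3. When the sign changes.** With compound symmetry and the full effect from Week 2, the coefficient is (Week 24 effect / earlier effect) - 7r/(1+7r). It is negative once that ratio falls below 4.2/5.2 = 0.81 (r = 0.6) to 5.6/6.6 = 0.85 (r = 0.8). The printed code would then be more conservative than the text.

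**4. 50 against 100 imputations.** Rubin's rules multiply the between-imputation variance by 1 + 1/m, which is 1.02 at m = 50 and 1.01 at m = 100. The numerical effect is negligible, but the plan should state one number. The analysis ANCOVA includes baseline weight. Omitting weight from the imputation code makes the imputation model poorer than the analysis model and different from 7.7.1.

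**5. Mixed model.** Change from baseline is 0 for every patient at the baseline visit. The baseline residual variance is therefore 0, the unstructured covariance is singular, and the baseline rows carry no information. Suppose the fit is salvaged from the Week 24 change alone. With equal variances at the two visits and baseline-to-Week 24 correlation r, the SE relative to the 7.7.2 model is 1/sqrt((1+r)/2): 1.118, 1.085 and 1.054 for r = 0.6, 0.7 and 0.8.

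**The case against.** The strongest reply is that 11.5 is headed as sample code and plainly is a template. It contains an empty placeholder in a CLASS statement, an unopened placeholder in the mixed-model ESTIMATE lines, and a Cox MODEL statement with nothing after the equals sign. The methods are stated in 7.7.1, 7.7.2, 7.8.1 and Table 6, and a competent programmer would follow them. This stands as a reason for low severity. It does not remove the mismatch: the Week 24 omission is repeated in two lists, and nothing in the SAP ranks text above code.

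A second reply is that the direction of the Week 24 error is not established. That also stands. The favourable direction needs both the software assumption and an effect that persists to Week 24.

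A reader might infer something stronger from the pVO2 placebo-based steps. They pool placebo patients with treatment non-completers and reuse a model containing arm, and 7.7.2 makes this imputation primary if 10% or more of data are missing, or 5% or more for reasons related to IP. The primary conclusion might then seem at risk. The documents do not support that. SAP 7.7.2 and Protocol 9.4.2 both require a model built on observed placebo data, and Table 6 places discontinuers in the placebo arm. How arm is to be handled is therefore largely answered, and the steps need only a clearer wording.

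**Conclusion.** The point holds as a correctable mismatch between text and code, at low severity (COULD). The list comparison is certain and rests on no assumption: as printed, Step 2 does not apply the placebo model at Week 24; the pVO2 imputation code has the wrong number of imputations and lacks weight; and the mixed-model code is degenerate.

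The size is small and conditional. It is about 1-5% of the effect too favourable in the Week 24 sensitivity estimates for KCCQ-CSS and LVOT-G, given regression imputation with arm, visit correlations of 0.6-0.8, an effect complete by Week 12 and maintained, and 5-10% dropout. The dropout range is assumed; the only missing-data rate the documents give is 10%, for pVO2. Should the effect wane, the error can go the other way.

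It should not be inferred that the confirmatory tests of these endpoints change. They come from MMRM on observed data, and Week 12 is in every list. Nor is any effect on the primary pVO2 conclusion shown.

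**What to change.** In SAP 11.5:

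- Add `<var week24>` to both the `monotone reg` list and the placebo-restricted model list in Step 2.
- In the primary pVO2 imputation code, set 100 imputations and add baseline weight. Make the same changes in the tipping-point code, which shows the same two gaps, and correct the reference to 50 datasets at the combining step.
- In the mixed-model code, use the pVO2 value at baseline and Week 24 as the response.
- As a minor clarification, state in the pVO2 placebo-based steps that the model for placebo patients and aficamten discontinuers is fitted to observed placebo-arm data without an arm term, as 7.7.2, Protocol 9.4.2 and Table 6 imply.

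A sentence saying that the SAP text governs over the sample code would be a useful safeguard. The cost is a few lines of SAP text before database lock, with no new data.

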7.7.3. Subgroup Analyses for the Primary Endpoint

Subgroup analyses will be performed by including the subgroup effect and subgroup by treatment interaction terms to the primary ANCOVA model for the primary endpoint. For subgroup analysis for the primary estimand, missing data imputed in the primary analysis will be used in the subgroup analyses. Only summary statistics will be presented for the subgroup level when the number of subjects in either treatment arm is ≤ 15 at this level. LSM estimate of the treatment difference, 95% confidence intervals for the mean treatment difference and nominal p-values will be provided for each subgroup level.

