7.9.1. Analysis of the Exploratory Efficacy Endpoint

The same ANCOVA model specified for the primary endpoint will be used to analyze the endpoints from CPET and continuous CMR measurements that are only assessed once post randomization. Body weight will not be included in the model to analyze CMR parameters. The same MMRM model will be used to analyze the continuous endpoints measured at multiple visits post randomization. CMH test stratified by randomization factors will be used analyze endpoints evaluation proportion of responders or binary outcomes.

Proportion of responders at each week will be summarized. Responders that are defined based on NYHA classification or LVOTs will be assigned after data handling in case there are missing NYHA class or LVOT assessments. Missing NYHA classification or LVOT value will be imputed the same way as that for the secondary endpoints that are based on NYHA classification or LVOT value. Patient will be treated as non-responder if patient's response status can't be determined due to the missing NYHA classification or LVOT assessments (after the imputation above) or clinical visits not performed after the patient early terminates from the study. Proportion of responders will be analyzed using Cochran–Mantel–Haenszel (CMH) test stratified by randomization factors. The p-value and 95% CI will be obtained using exact method. Proportion of patients remaining SRT eligible at Week 24 will be analyzed using logistic model regression model stratified by beta blocker use/non-use adjusting for significant baseline characteristics. The model will include treatment as fixed effect and baseline characteristics as covariates. Covariates measured as continuous will be introduced to the model as continuous variable. Stepwise model selection method will be used based on the default stay or entry level of 0.05 to evaluate significant baseline covariates. Supportive analysis using CMH stratified by randomization factor (beta-blocker use/non-use) will be performed. Another supportive analysis of proportion of patients SRT eligible at each visit will be provided using a repeated measure logistic regression model with treatment, visit, treatment by visit and significant baseline characteristics from the model above. Time to first SRT ineligible in patients who are SRT eligible at baseline will be analyzed using Kaplan-Meier method.

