For NT-proBNP and hs-cardiac-TnI, the log transformed proportional change will be analyzed using a MMRM model with log baseline as covariate, treatment group, randomization stratification factors, visit, log baseline by visit and treatment by visit interaction as fixed effects. Log transformed proportional change in Valsalva and resting LVOT will be analyzed using the

same model. Geometric LS Means estimate and ratio of proportional change in NT-proBNP and hs-cardiac-TnI between aficamten vs. placebo, 95% CI of ratio and p-value will be presented. Median and median difference of NT-pro-BNP and hs-cardiac- Tnl between treatment group and 95% confidence of the median difference will be presented at Week 12 and 24. Time to 1 mm ST depression at Week 24 will be analyzed using Cox regression model with treatment, randomization stratification factors as fixed effect. Patients didn't experience 1 mm ST depression will be censored at the end of CPET exercise. Logistic regression model will be fit to LVH strain pattern on ECG for Week 12 and 24, separately. The model will include baseline LVH pattern, stratification factors and treatment. Difference in proportion of patients with no LVH will be estimated and 95% CI for odds ratio (aficamten vs. placebo) and its corresponding p value will be obtained.

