where trtid is assigned as 0 at baseline, 0 for placebo group at Week 24 and 1 for active group at Week 24. &c1 and &c2 are the proportion of patients evaluated in each stratification level among all the patients.

Subgroup analysis for the primary endpoint

```
proc mianalyze parms=mixparms covb(effectvar=rowcol)=mixcovb;  
  class <treatment arm> <beta blocker use> <exercise modality> <subgroup> ;  
  =<base pvo2 > <base weight> <treatment arm> <beta blocker use> <Exercise modality>  
  modeleffects Intercept <base pvo2 > <base weight> <treatment arm> <beta blocker use>  
  <Exercise Modality> <subgroup>*<treatment arm>;  
run;
```

SAS codes to evaluate normality assumption for the primary endpoint

The normality assumptions for the ANCOVA analysis will be assessed by residual illustration. The outpred option in the above code stores residuals which are used to test the assumption of normality. Examination of residuals can be done using the following codes.

```
proc univariate data=work normal;  
var ScaledResid; QQPLOT ScaledResid;  
ods output QQPlot=qqplot;  
run;
```

SAS codes to perform CMH test

```
proc freq data=work;  
  tables <Beta blocker use>*<CPET modality>*<treatment arm>*<response Y/N>/CMH  
  exactcmh;  
  exact riskdiff (column=2) relrisk (column=2) commor.  
Run;  
where response is coded as Y=1, N=0.
```

SAS codes to rank observation

```
proc rank data=work out=rwork nplus1;  
Var chg;  
Ranks rchg;  
Run;
```

SAS code for proportional hazard Cox regression model

```
Proc phreg data=work;  
  Class <treatment arm>(ref=first) ;  
  Model <time>*< censor (1)>= ;  
  Strata <beta blocker use> <CPET modality> ;  
Run;
```

SAS code for stratified logistics regression model

```
Proc phreg data=work;  
  Class <treatment arm>;  
  Model <Response> (event='Y')= <treatment arm> <baseline covariates>/selection=stepwise  
  details;  
  Strata <beta blocker use> ;  
Run;
```

SAS code for EQ-5D-5L Index Value

```
*****  
*SAS syntax code for the computation of index*  
*values with the US TTO value set*  
*****  
  
data WORK.CAT;  
set WORK.CAT;  
  
if mobility eq 1 then disut_mo=0;  
else if mobility eq 2 then disut_mo=0.096;  
else if mobility eq 3 then disut_mo=0.122;  
else if mobility eq 4 then disut_mo=0.237;  
else if mobility eq 5 then disut_mo=0.322;  
  
if selfcare eq 1 then disut_sc=0;  
else if selfcare eq 2 then disut_sc=0.089;  
else if selfcare eq 3 then disut_sc=0.107;  
else if selfcare eq 4 then disut_sc=0.220;  

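### SAP 11.5 sample code departs from the SAP text in two exploratory models and the primary-endpoint subgroup analysis; treatment can be selected out, is absent, or is not estimated per subgroup level

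*SAP*

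**What the plan says.** The text of the SAP is clear for all three analyses.

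- **Week 24 SRT eligibility (7.9.1).** A logistic model stratified by beta-blocker use: "The model will include treatment as fixed effect and baseline characteristics as covariates". Stepwise selection at 0.05 is there to find significant baseline covariates.
- **Time to 1 mm ST depression (7.9.1).** To be "analyzed using Cox regression model with treatment, randomization stratification factors as fixed effect".
- **Primary-endpoint subgroups (7.7.3, and likewise 7.5).** Analyses are "performed by including the subgroup effect and subgroup by treatment interaction terms to the primary ANCOVA model". A treatment difference, 95% confidence interval and nominal p-value are promised for each subgroup level.

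The sample code in 11.5 says something else.

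- **Stratified logistic block.** Headed as logistic regression, it calls PROC PHREG with "Model <Response> (event='Y')= <treatment arm> <baseline covariates>/selection=stepwise".
- **Cox block.** "Class <treatment arm>(ref=first", then "Model <time>*< censor (1)>=" with nothing before the semicolon, then "Strata <beta blocker use> <CPET modality>".
- **Subgroup block.** A PROC MIANALYZE step whose list of effects ends in "<Exercise Modality> <subgroup>*<treatment arm>" and does not name the subgroup on its own.

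**The concern.** A programmer who works from the appendix instead of Section 7 would get results that the text does not describe. The logistic block is the one that can mislead without notice. Its mixed syntax has to be repaired before it runs, and the obvious repair, changing the procedure name, leaves treatment subject to selection. The treatment effect would then appear only in datasets where it passed the 0.05 threshold, so any reported odds ratio would be conditional on significance. The Cox block as printed gives no treatment estimate. The subgroup block does not lead to the per-level differences that 7.7.3 promises, and its pooled interaction term invites a reading as a test of effect modification.

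**Working it through.** The plan states no figure on this point, so there is none to reproduce. Each block was set against its text term by term, and the consequences were then sized.

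**1. Stratified logistic block**

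The text keeps treatment in the model. The code lists it beside the baseline covariates under stepwise selection, with no INCLUDE= option.

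Under no treatment effect, a candidate tested at 0.05 enters about 5% of the time, so treatment is left out about 1 − 0.05 = 95% of the time.

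With a real effect, P(left out) ≈ 1 − power of a two-sided 0.05 comparison of two proportions, with n per arm:

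power = Φ{ [|p₁ − p₂| − 1.96·√(2p̄(1 − p̄)/n)] / √[(p₁(1 − p₁) + p₂(1 − p₂))/n] }

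Example: 40 patients (n = 20 per arm), 60% v 40% still eligible, p̄ = 0.5. Then (0.2 − 1.96 × 0.158)/0.155 ≈ −0.71, power ≈ 0.24, and P(left out) ≈ 0.76.

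The documents give neither the number eligible at baseline nor the rates, so everything in this table is an assumption:

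| Eligible at baseline, both arms | 60% v 40% | 60% v 30% | 60% v 20% |
|---|---|---|---|
| 40 | 76% | 52% | 25% |
| 60 | 66% | 35% | 9% |
| 80 | 57% | 22% | 3% |
| 100 | 48% | 13% | 1% |

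The approximation ignores the stratification and the other candidates.

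**2. Cox block**

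A CLASS statement declares a variable as categorical but adds no effect to the model. With nothing to the right of the equals sign the model has zero parameters, so no hazard ratio is estimated. Separately, beta-blocker use and CPET modality are in STRATA, where 7.9.1 makes them fixed effects.

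**3. Subgroup block**

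PROC MIANALYZE pools estimates and fits nothing. The only printed step that writes the datasets it reads (mixparms and mixcovb) is the primary ANCOVA, whose MODEL statement has baseline pVO₂, baseline weight, treatment and the two stratification factors. It has no subgroup and no interaction term. No printed statement forms a treatment difference within a subgroup level. A stray line beginning with an equals sign also breaks the syntax.

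Does leaving out the subgroup main effect matter? Take a two-level subgroup with cell means α + τt + βs + γts. Treatment and subgroup are both CLASS variables, so without the main effect the interaction term carries a separate subgroup difference for each arm: δ₀ = β on placebo and δ₁ = β + γ on active drug.

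- Treatment difference in level 0: τ.
- Treatment difference in level 1: τ + δ₁ − δ₀ = τ + γ.
- Joint 2-df test of the term: δ₀ = δ₁ = 0, that is, β = 0 and γ = 0 together.

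So the per-level differences are unchanged, but the term's test also picks up the prognostic effect β.

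A simulated dataset confirms this. It used n = 270, SD 3.5 and treatment effect 1.5 from SAP 3.3.1, with an assumed subgroup effect of 1.0 and interaction of 0.5:

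| | With main effect | Without, CLASS coding |
|---|---|---|
| Treatment difference, level 0 | 1.556 | 1.556 |
| Treatment difference, level 1 | 2.647 | 2.647 |
| SE, level 0 | 0.6215 | 0.6215 |
| Residual sum of squares | 3318.317 | 3318.317 |
| Test of subgroup-by-treatment term | p = 0.212 (1 df) | p = 0.013 (2 df) |

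The 1-df contrast δ₁ − δ₀ from the second fit again gives p = 0.212. In 1000 further datasets with no interaction and an assumed subgroup effect of 1.5 mL/kg/min, the 2-df term rejected in 91% and the proper 1-df test in 6%.

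**The case against.** The section is labelled as sample code and uses generic placeholders; Section 7 holds the methods and is unambiguous. SAP 7.1 puts exploratory endpoints and subgroups at nominal 0.05 without multiplicity adjustment, and none of the three blocks feeds the 11-step hierarchy in 7.6. All of this stands and limits the point to a minor one.

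For the logistic block, it can be said that code which does not run cannot drop anything, and that 7.9.1 also plans a supportive CMH test and a repeated-measures logistic model containing treatment. Both are true. The 95% figure therefore applies only if someone repairs the procedure and leaves the MODEL statement alone, and the endpoint would not be left with a selected estimate as its only result.

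For the Cox block, placeholders elsewhere in 11.5 are visibly damaged (an empty bracket pair in the tipping-point CLASS list, a missing opening bracket in the CPET mixed model). A treatment term may have been lost in extraction. That cannot be settled from the text. A missing hazard ratio would also be noticed at once. The use of STRATA against the text's fixed effects does not depend on this question.

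For the subgroup block, a reader might infer that omitting the subgroup main effect biases the subgroup treatment differences. The documents do not support that: both variables are in CLASS, so a fit without the main effect is only reparameterized. If the upstream fit contains the main effect, as 7.5 and 7.7.3 require, not pooling its coefficient changes nothing. Bias arises only with numeric 0/1 coding (1.23 and 2.95 instead of 1.56 and 2.65 in the same dataset), which the SAP does not use. Nor does 7.7.3 promise a test of the pooled interaction term; the planned global interaction test is a separate model in 7.7.4.

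**Conclusion.** The mismatch between code and text holds in all three blocks, with different consequences. It is minor.

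- **Logistic:** the most substantive. The code lets selection act on treatment, which the text does not. If only the procedure is corrected, treatment is left out about 95% of the time under no effect, and between 1% and 76% of the time over the assumed sizes and rates above.
- **Cox:** no treatment estimate as printed, subject to the extraction caveat, and stratification where the text says adjustment.
- **Subgroups:** no printed fit contains the subgroup terms and no statement yields the required per-level differences. The subgroup-by-treatment term without its main effect must not be read as an interaction test.

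Two wider inferences are not supported. First, no primary or secondary test is affected. In particular, 7.8.1 also uses stepwise selection for the duration of SRT eligibility, but it keeps treatment as a fixed effect, and 11.5 prints no model code for that analysis. Second, the point is not a case against stepwise selection of baseline covariates, which 7.9.1 prespecifies.

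**What to change.** - **Logistic:** use PROC LOGISTIC with beta-blocker use in STRATA and force treatment in (for example, list it first with INCLUDE=1). Keep the prespecified stepwise selection for the baseline covariates.
- **Cox:** put treatment, beta-blocker use and CPET modality in the MODEL statement, as 7.9.1 states, and remove the STRATA statement.
- **Subgroups:** print an ANCOVA with subgroup and subgroup-by-treatment added, fitted in each imputed dataset. Form the treatment difference at each level and the interaction contrast there, then pool those estimates and standard errors. Delete the stray line.

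The cost is a few lines of template code. The changes bring the code into line with the existing text, so no analysis method changes. By SAP 5.4 only a substantial deviation in methods calls for an SAP revision or a CSR note, so correcting the programming specification before database lock should be enough.
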